10.2.4 Sample Size Determination

Up to 105 patients in total will be randomized to 1 of 2 treatments (70 patient to MGL-3196, 35 patients to placebo). It is estimated that the treatment difference of percent change in LDL-C from baseline to Week 12 between any dose of the MGL-3196 group and the placebo group is about -20%. With a common standard deviation for the change in LDL-C at 20%, 27 patients per group to complete the Week 12 visit will provide 90% power with a two-sample t-test. The significance level is set as 0.025 for the consideration of multiplicity in comparisons of 2 daily dosing regimens of MGL-3196 vs. placebo group. The enrollment size is designed to allow for dropouts before the 12-week visit, and as such, patients who drop out of the study will not be replaced.

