3.7.3 Subgroup Analysis of LDL-C

The subgroup analysis of LDL-C will be based on the mITT population. Since the analyses are for descriptive purposes only, no adjustments will be made for multiplicity.

The analysis of LDL-C will be performed based on MGL-3196 exposure group. In the analysis of LDL-C based on MGL-3196 exposure group, the patients who are taking MGL-3196 will be categorized into higher and lower exposure groups. The same ANOVA and ANCOVA models will be used, with pairwise comparisons between each exposure group versus placebo will be provided.

The analysis of LDL-C will also be performed based on SHBG group. In the analysis of LDL-C based on SHBG group, the patients who are taking MGL-3196 will be categorized into groups with higher increase or lower increase of SHBG from baseline to Week 12. Patients who are taking MGL-3196 but do not have Week 12 SHBG values will not be included. The same ANOVA and ANCOVA models will be used, with pairwise comparisons between each exposure group versus placebo to be provided.

The final dose of MGL-3196 (100 mg or 60 mg) will also be used to repeat the primary efficacy analysis. Similar to the exposure group, an analysis will be performed, but with the final dose of MGL-3196 to categorize patients who are taking MGL-3196.

The primary efficacy analysis of LDL-C will be repeated based on the following subgroups:

- Statin subgroup (80 mg Atorvastatin, 20/40 mg Rosuvastatin, or No/Low Dose Statin);
- Exposure group, SHBG group, in combination with statin subgroup;
- Gender subgroup (male, or female);
- Exposure group, SHBG group, in combination with gender subgroup;
- Baseline LDL-C value (<100 mg/dL, or \geq 100 mg/dL);
- Statin and baseline LDL-C subgroup;

- Exposure group, SHBG group, Final MGL-3196 dose group, in combination with baseline LDL-C subgroup;
- Baseline BMI value (<25 kg/m², or ≥25 kg/m²; and <30 kg/m², or ≥30 kg/m²);
- Exposure group, SHBG group, Final MGL-3196 dose group, in combination with baseline BMI subgroup;
- Average TSH between baseline and screening subgroup (<2 mIU/L, or ≥2 mIU/L);
- Exposure group, SHBG group, Final MGL-3196 dose group, in combination with average TSH between baseline and screening subgroup;

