3.8.2 Clinical Laboratory Assessments

3.8.2.1 Chemistry and Hematology

Descriptive statistics of each chemistry and hematology parameter will be presented for baseline values and for values and changes from baseline at each post-baseline visit. These will be presented by treatment group for each parameter using the Safety Population.

Counts and percentages of patients with any post-baseline observation that is below the lower limit of normal (<LLN) or above the upper limit of normal (>ULN) will be summarized for each chemistry and hematology parameter by treatment group and overall.

The liver enzyme parameters (ALT, AST, creatine kinase [CK], and GGT) will be analyzed for the overall Safety Population by active and placebo groups, and by exposure group, final dose group, and SHBG group. Statin subgroup will also be explored. Patients with mild liver diseases will not be included in the analysis of liver enzyme parameters, since the liver enzyme value will be affected. The possible liver disease may include, but is not limited to: elevated

liver enzymes (elevated direct bilirubin ≥ 0.3 mg/dL, or GGT > 100 U/L) or large amount of alcohol use.

The shift from baseline value to the worst post-baseline value will be summarized for selected parameters (AST, ALT, total bilirubin, alkaline phosphatase, creatinine, and CK). Shift categories will be based on normal ranges (<LLN, Normal, >ULN).

3.8.3 12-Lead Electrocardiogram

ECG parameters (heart rate, PR interval, QRS interval, QT interval, QTcB interval, QTcF interval, RR Interval, and overall interpretation) will be summarized by treatment group using descriptive statistics for the Safety Population. The average of 3 readings will be used in the summaries. For the overall interpretation, the most severe interpretation at the visit will be summarized. The count and percentage of patients with QTcF and/or QTcB above thresholds (>450 msec, >480 msec, >500 msec) or change from baseline above thresholds (>30 msec, >60 msec) will be summarized by treatment group for the Safety Population.

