4. SAMPLE SIZE DETERMINATION

Up to 105 patients in total will be randomized to 1 of 2 treatments (70 patients to MGL-3196, 35 patients to placebo). It is estimated that the treatment difference of percent change in LDL-C from baseline to Week 12 between any dose of MGL-3196 group and the placebo group is about -20%. With a common standard deviation for the change in LDL-C at 20%, 27

patients per group to complete the Week 12 visit will provide 90% power with a two-sample t-test. The significance level is set as 0.025 for the consideration of multiplicity in comparisons of 2 daily dosing regimens of MGL-3196 vs. placebo group. The enrollment size is designed to allow for dropouts before the 12-week visit, and as such, patients who drop out of the study will not be replaced.

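### Comparing SHBG-response groups of the active arm with all placebo does not give valid tests of treatment effect; error exceeds 5% if SHBG rise and LDL-C fall are correlated

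*SAP*

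**What the plan says.** SAP 3.7.3 has the MGL-3196 patients "categorized into groups with higher increase or lower increase of SHBG from baseline to Week 12". Placebo patients are not sorted. For the active arm only, "Patients who are taking MGL-3196 but do not have Week 12 SHBG values will not be included". The ANOVA and ANCOVA models of SAP 3.7.2 are reused with pairwise comparisons against placebo. The SHBG paragraph speaks of exposure groups at this point; I read it as the SHBG groups. The sample code in 3.7.2 requests least-squares means, confidence limits and p-values against placebo.

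SAP 3.1 gives a fixed cut: an increase of at least 140% versus less than 140%. The marker's name is redacted there, and I read it as SHBG from 3.7.3. Protocol 9.8 schedules SHBG at Baseline and Week 12, among other visits.

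The grouping is reused in three places:
- SAP 3.7.3 crosses SHBG group with statin, gender, baseline LDL-C, BMI and TSH subgroups.
- SAP 3.7.5 applies a group whose name is redacted, apparently the same one, to all secondary and exploratory endpoints.
- SAP 3.8.2.1 analyzes liver enzymes and CK "by exposure group, final dose group, and SHBG group", without naming a model or test.

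SAP 3.7.3 calls the subgroup analyses descriptive and makes no multiplicity adjustment. The primary analysis in 3.7.2 is all MGL-3196 versus placebo and does not use SHBG.

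**The concern.** A comparison with placebo is causal because the two arms were alike at randomization. Sorting one arm on something that happens afterwards breaks this. Anything that affects both SHBG rise and LDL-C change, such as adherence that extends to the statin, gathers patients with better LDL-C results in one active group and those with worse results in the other. Each group then faces a placebo arm that contains both kinds. The ANCOVA removes only the part of the imbalance that baseline LDL-C explains.

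Missing data are also handled unequally. A placebo patient without a Week 12 LDL-C value stays in through LOCF, while an active patient without Week 12 SHBG leaves.

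At stake is the reading of the higher-SHBG result as a treatment effect with a p-value attached. The lower-SHBG result could likewise be read as evidence of little or no effect.

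**Working it through.** **1. The plan's own figure.** The documents state no error rate for the SHBG analysis. The nearest figure is the sample size.
- Inputs: "The significance level is set as 0.025 for the consideration of multiplicity in comparisons of 2 daily dosing regimens"; "27 patients per group to complete the Week 12 visit will provide 90% power with a two-sample t-test"; a difference of about -20 in "the treatment difference of percent change in LDL-C from baseline to Week 12"; "With a common standard deviation for the change in LDL-C at 20" percent; "70 patients to MGL-3196, 35 patients to placebo". I take 0.025 as two-sided, since sidedness is not stated.
- Normal approximation: n = 2 × (SD/difference)² × (2.241 + 1.282)² = 2 × 1 × 12.41 = 24.8, so 25 per group.
- Noncentral t: power is 0.898 at n = 26 and 0.910 at n = 27, so 27 is reproduced.

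This confirms the SD and arm sizes used below; it does not bear on the SHBG point itself.

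**2. Assumptions not in the documents.** The within-arm correlation ρ between SHBG rise and LDL-C fall, the share of active patients above the 140% cut, and the rate of missing Week 12 SHBG. Each is varied.

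**3. False shift by formula, with no LDL-C effect.** For bivariate normal data split evenly, the mean of the upper half is 0.798 SD above the center. The shift is therefore ρ × 20 × 0.798 percentage points, in favor of the drug in the higher group and against it in the lower.
- ρ = 0.2: 3.2 points; ρ = 0.3: 4.8 points; ρ = 0.5: 8.0 points.
- Standard error, 35 versus 35: 20 × √(1/35 + 1/35) = 4.78.
- At ρ = 0.3 the ratio is 4.79/4.78 = 1.00. Two-sided error = P(Z > 0.96) + P(Z < -2.96) = 0.17.

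**4. Simulation.** 20,000 trials per scenario; three-group ANOVA with pooled variance; each SHBG group against all placebo at two-sided 0.05; even split; no LDL-C effect.

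| ρ | Higher group | Lower group | Either | Shift, higher / lower (points) |
|---|---|---|---|---|
| 0 | 4.8% | 5.0% | 8.8% | 0 / 0 |
| 0.1 | 6.4% | 6.2% | 11.8% | -1.6 / +1.5 |
| 0.2 | 10.4% | 10.6% | 20.3% | -3.2 / +3.2 |
| 0.3 | 17.1% | 17.4% | 33.8% | -4.8 / +4.8 |
| 0.5 | 41.7% | 41.3% | 73.6% | -8.0 / +8.0 |

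The formula agrees at 0.2 and 0.3 (10% and 17%). At 0.5 it gives 39%, a little low, because sorting also narrows the spread within each group. All active versus placebo held 5.2%, 5.1% and 4.9% at ρ = 0, 0.3 and 0.5.

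**5. Share above the cut, ρ = 0.3.** With 30% above, error is 24.2% in the higher group and 10.4% in the lower. With 70% above, it is 10.4% and 24.7%. The smaller group has the larger error.

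**6. One-sided exclusion.** At ρ = 0:
- 10% missing at random leaves about 5%.
- 10% missing, with missingness correlated 0.3 to 0.5 with poor LDL-C response, gives about 6–7% per group (shift -1.2 to -2.0 points).
- 20% missing on the same terms gives about 7–11%.

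At ρ = 0.3 with 10% missing and missingness correlation 0.5, error is 26.8% in the higher group and 8.5% in the lower.

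**7. With the planned -20 effect.** Adding the shifts for ρ = 0.2 to 0.5 gives about -23 to -28 in the higher group and -17 to -12 in the lower. This treats ρ as arising from differences between patients other than in the drug's own LDL-C effect.

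**The case against.** Four arguments weigh against the point.

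- **The analysis is labelled descriptive and the primary comparison does not use SHBG.** This limits the consequence and stands. But the label is offered as the reason for not adjusting for multiplicity. It does not remove the p-values the models produce, and the problem here is bias, which no multiplicity adjustment corrects.
- **The correlation needs a source.** If the drug has no LDL-C effect, taking more of it cannot by itself link SHBG rise to LDL-C fall. Some other shared cause is needed, for example adherence that also covers the statin, or individual effects that average to zero. This stands, and it is why no single inflation figure can be given. If the drug works, part of the gap between groups may be real variation in effect. The trial cannot separate that part, because nobody knows which placebo patients would have fallen in each group.
- **The exclusion follows from the split.** A patient without the classifying value cannot be classified. That is true, and those patients remain in the primary analysis if they meet its entry conditions. The exclusion is therefore secondary.
- **No conclusion need reverse.** Under the planned effect and these assumptions, both groups still show reductions. That stands too; the error is in the size and in the contrast between groups.

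A reader might infer that the SHBG groups would come out significant even for an inert drug. The figures do not support this: at ρ up to 0.5, fewer than half of null trials are significant for a given group under an even split, and at ρ = 0 the error is nominal. Nor would both groups falsely favor the drug through the split, since the shifts run in opposite directions. A reader might also take SAP 3.8.2.1 to plan pairwise safety tests; it names none.

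**Conclusion.** The point holds in conditional form. Comparing SHBG-response groups with all placebo does not give a valid test of treatment effect, because the groups are formed from a post-randomization response in one arm only. Under an even split with SD 20, 70 active and 35 placebo patients and no LDL-C effect, per-group error is about 5%, 10%, 17% and 42% at correlations 0, 0.2, 0.3 and 0.5. The corresponding false shifts are about 0, 3, 5 and 8 points, in favor of the drug in the higher group and against it in the lower. The correlation, the share above 140% and the missing rate are all assumptions, so the size in this trial cannot be fixed. The ANCOVA version was not simulated. The unequal exclusion adds bias only if missingness is related to response. The primary result is untouched, so this is a minor point that is cheap to correct.

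**What to change.** In SAP 3.7.3, delete the comparisons of SHBG groups with placebo, including those crossed with other subgroups. Do the same in SAP 3.7.5 if the redacted group there is SHBG. In their place, within the MGL-3196 arm only, regress percent change in LDL-C on continuous SHBG change, adjusted for baseline LDL-C. Report the slope with its confidence interval, label it a non-causal association, and state how many patients were excluded for missing Week 12 SHBG.

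Applying the 140% cut to both arms is not a safe substitute. In simulation it held about 5% error only when the drug did not shift SHBG; if the drug raises SHBG, the two groups above the cut are no longer alike.

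The cost is SAP wording and fewer tables. The sponsor loses the SHBG-group-versus-placebo p-values and keeps the biomarker relation.

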10.2 Statistical Methods

10.2.1 Analysis of Efficacy

10.2.1.1 Primary efficacy analysis

The primary efficacy variable will be the change in LDL-C from baseline to Week 12. Summary statistics (number of patients, mean, standard deviation, median, minimum, and maximum) at all visits and change from baseline will be provided. The primary efficacy analysis will be analyzed with an analysis of covariance (ANCOVA) model with treatment as a factor and baseline LDL-C as a covariate. Determinations for the 100 (and 60) mg groups will be based on all 12 weeks of the study, including the first two weeks (Week 0-2) in which all patients were on 100 mg and the second two weeks (Week 2-4) when all patients down-titrated to 60 mg. The assigned group (60 or 100 mg) will be based on the dose at Week 4 to Week 12. For any patients in the ITT Population with a missing primary efficacy parameter, the last observation carried forward method will be used. The multiplicity (MGL-3196 100 mg versus placebo and MGL-3196 60 mg versus placebo) will be controlled by Dunnett's Test. The primary efficacy analysis will be performed based on the ITT Population and repeated based on the Per Protocol Population.

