2. STUDY OBJECTIVES AND STUDY DESIGN

2.1 Study Objectives

2.1.1 Primary Objective

The primary objective of this study is to determine the effect of each of two separate treatment groups (the “100 mg group” and the “60 mg group”) of once-daily oral dose of MGL-3196 and matching placebo on the percent change from baseline in low-density lipoprotein cholesterol (LDL-C) in patients with heterozygous familial hypercholesterolemia (HeFH).

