3.7.2 Primary Efficacy Analyses of LDL-C

The primary efficacy variable will be the percent change in LDL-C from baseline to Week 12. Summary statistics (number of patients, mean, standard deviation, median, minimum, and maximum) at all visits and change and percent change from baseline will be provided.

The primary efficacy variable, the percent change in LDL-C from baseline to Week 12, will be analyzed using an analysis of variance (ANOVA) model with treatment (MGL-3196 or placebo) as a factor based on the mITT population. For any patients in the mITT Population with a missing primary efficacy variable, the last post-baseline observation carried forward (LOCF) method will be used. The least-squares mean, 95% confidence interval, and p-value will be provided for the comparison of MGL-3196 versus placebo.

Sample SAS® code is provided below:

```
*****

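### The SAP keeps the 100 mg and 60 mg effects as its primary objective but compares each dose with placebo without the Dunnett control set in the protocol; read at 0.05, the two tests have about a 9% family-wise error rate

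*SAP*

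**What the plan says.** Protocol 10.2.1.1 makes the two dose groups the primary comparisons and states how the error is controlled: "The multiplicity (MGL-3196 100 mg versus placebo and MGL-3196 60 mg versus placebo) will be controlled by Dunnett's Test". The protocol synopsis says the same.

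The SAP is divided on the point:

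- Section 2.1.1 leaves the primary objective unchanged: "to determine the effect of each of two separate treatment groups", named there as the 100 mg and 60 mg groups.
- Section 3.7.2 fits an "analysis of variance (ANOVA) model with treatment (MGL-3196 or placebo) as a factor based on the mITT population". Its reported output is one contrast: "The least-squares mean, 95% confidence interval, and p-value will be provided for the comparison of MGL-3196 versus placebo".
- Section 3.7.3, on subgroups, holds the only analysis of LDL-C by dose: "The final dose of MGL-3196 (100 mg or 60 mg) will also be used to repeat the primary efficacy analysis". It follows the exposure-group analysis, in which each group is compared pairwise with placebo. The rule for the whole section is: "Since the analyses are for descriptive purposes only, no adjustments will be made for multiplicity".
- Section 4 sizes the trial for two dose comparisons: "The significance level is set as 0.025 for the consideration of multiplicity".

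Dunnett's test is not mentioned in the SAP. No testing order links the pooled test to the dose comparisons.

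**The concern.** The pooled contrast cannot show the effect of each dose group. A reader who wants to know whether the stated primary objective was met has to turn to the final-dose analysis in SAP 3.7.3, where the protocol's error control has been removed without comment.

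Three rules can now be read for the same two comparisons: Dunnett (protocol), 0.025 each (SAP section 4) and no adjustment (SAP 3.7.3). A dose-group p-value between about 0.027 and 0.05 fails under the protocol and under section 4. It would look positive to anyone applying the conventional 0.05 that the 95% intervals suggest. What is at stake is any claim about an individual dose. The pooled result is not at risk.

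**Working it through.** **Inputs.** From the sample-size sections (Protocol 10.2.4, SAP 4): difference 20 points, SD 20, level 0.025, 27 completers per group, 90% power, 70 patients on MGL-3196 and 35 on placebo. The size of the 60 mg group is not given. As a guide, Protocol 1.2.2 expects about 25 to 30% of patients above target exposure at 100 mg: 0.25 × 70 = 17.5 and 0.30 × 70 = 21, so roughly 18 to 21 patients. Using that share for the 60 mg group is an assumption, so a range of splits is shown.

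**Step 1: the plan's own figure.** For a two-sample t-test with n = 27 per group, the noncentrality is (20/20)/√(2/27) = 3.67 on 52 df. The two-sided 0.025 critical value is 2.308. Power is 91.0%; n = 26 gives 89.8%. So 27 is the smallest n that reaches 90%. The stated figure reproduces, with 0.025 taken as a two-sided level for each dose comparison.

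**Step 2: correlation of the two dose tests.** Both use the same placebo group, so with placebo size n0 and dose-group sizes n1 and n2,

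ρ = √[ n1/(n1+n0) × n2/(n2+n0) ].

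For 35/35/35, ρ = √(0.5 × 0.5) = 0.50. For 35/52/18, ρ = √(52/87 × 18/53) = √(0.598 × 0.340) = 0.45.

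**Step 3: family-wise error under the global null.** This is P(max(|t1|, |t2|) > c), with a pooled variance on n0+n1+n2−3 df, by simulation of 6 million trials per setting. The last digit can move by one between runs. The last column counts a rejection by the pooled test at 0.05 or by either Dunnett-adjusted dose test.

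| Placebo / 100 mg / 60 mg | ρ | Each test at 0.05 | Each test at 0.025 | Dunnett critical t (per-comparison p) | Dunnett beside an ungated pooled test at 0.05 |
|---|---|---|---|---|---|
| 35/35/35 | 0.50 | 9.0% | 4.6% | 2.24 (0.027) | 6.8% |
| 35/49/21 | 0.47 | 9.1% | 4.7% | 2.25 (0.027) | 6.8% |
| 35/52/18 | 0.45 | 9.2% | 4.7% | 2.25 (0.027) | 6.8% |
| 27/27/27 | 0.50 | 9.1% | 4.6% | 2.25 (0.027) | 6.8% |
| 27/39/15 | 0.46 | 9.1% | 4.7% | 2.26 (0.027) | 6.8% |
| 35/60/10 (extreme) | 0.38 | 9.4% | 4.8% | 2.26 (0.026) | 7.0% |

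The upper bound, if the two tests were independent, is 1 − 0.95² = 9.75%.

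**Step 4: effect of a gate.** If the dose tests are interpreted only after the pooled test is significant at 0.05, a false claim of any kind requires the pooled test to reject first. Under the global null the total therefore cannot exceed 5%.

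**Step 5: cost of Dunnett.** With 102 df the unadjusted critical value is 1.983, and 2.243/1.983 = 1.13. The dose-group intervals become about 13% wider.

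**The case against.** The best defence is that the SAP has made one pooled comparison its primary test, which has no multiplicity of its own, and has openly labelled everything in 3.7.3 descriptive. It sets no decision rule there and no 0.05 test level. The only significance level the SAP states is 0.025, given for exactly these two comparisons, and that would hold the error below 5%. A reader might infer from 3.7.3 that the plan itself runs its primary comparisons at a 9% error rate, or that its primary result is inflated. The documents support neither reading. The 0.05 is inferred from the 95% intervals and the statement that nothing is adjusted, and the pooled test is not affected.

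What the defence does not remove is the conflict. The descriptive label covers the whole section, including the only two LDL-C contrasts that answer the objective in 2.1.1. The 0.025 sits in sample-size text, and 3.7.3 does not apply it. The sample code compares with a control but defines treatment at two levels and names no adjustment. It therefore does not settle how a three-level run would be handled, and the text of 3.7.3 governs.

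Two further objections stand as limits. The dose groups are formed after randomisation from the Week 2 drug level, so neither the 9% nor Dunnett's 5% is guaranteed if drug level is related to prognosis. And adding Dunnett beside an ungated pooled test would give about 6.8%, not 5%, so the remedy needs a stated order.

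**Conclusion.** The point holds as an inconsistency with a conditional cost. The objective and the sample-size level in the SAP rest on two dose comparisons, while its primary analysis is pooled and the dose comparisons have lost the protocol's control. If the dose p-values are read at two-sided 0.05 as evidence on the primary objective, the family-wise error is about 9% (9.0 to 9.2% over plausible splits, 9.4% at an extreme one). That compares with 5% under Dunnett and 4.6 to 4.7% at the level in section 4.

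This rests on three assumptions: the 0.05 reading, which the SAP does not state; a common variance; and exchangeability with placebo, under the null, of the groups defined by drug level. The result for MGL-3196 as a whole does not depend on this point. Claims about each dose do.

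**What to change.** In SAP 3.7.3, for the final-dose repeat of the primary analysis only:

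1. Fit placebo, 60 mg and 100 mg as three levels in one model, grouped by the dose assigned for Weeks 4 to 12 as in Protocol 10.1. SAP 2.2 allows down-titration to other doses, so a literal final dose need not be 100 mg or 60 mg.
2. Report Dunnett-adjusted p-values and simultaneous 95% confidence intervals for the two comparisons with placebo, and name the adjustment in the code.
3. State that these comparisons are interpreted only after the pooled test is significant at two-sided 0.05, so that the pooled and dose tests together stay within 5% under the global null.
4. Note that the error rate assumes the groups defined by drug level are exchangeable with placebo under the null.

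Leave the other 3.7.3 subgroups descriptive. Section 4 can stand, because 0.025 per comparison is slightly stricter than Dunnett's threshold of about 0.027.

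The cost is a few SAP sentences and one model specification, with dose-group intervals about 13% wider. The change does not resolve other differences between the documents, such as ANOVA against ANCOVA or the modified against the full intent-to-treat population.

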10.2.1.4 Subgroup analysis

Subgroup analysis of the primary efficacy variable and/or selected secondary/other efficacy variables may be performed, such as gender (male/female), body mass index (≥ 30 kg/m² or < 30 kg/m²), age group (\geq median or $<$ median), and baseline thyroid status.

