** PCHG = Percent change in LDL-C from Baseline to Week 12      **
** TRT = Treatment group where 0 = placebo, 1= MGL-3196           **
*****
PROC GLM;
  CLASS TRT;
  MODEL PCHG = TRT;
  LSMEANS TRT / e pdiff=control("0") cl;
RUN;
```

In addition to the percent change from baseline to Week 12 in LDL-C, the change in LDL-C from baseline to Week 12 will be analyzed using an analysis of covariance (ANCOVA) model with treatment as a factor and the baseline value as a covariate. For any patients in the mITT Population with a missing primary efficacy variable, the LOCF method will also be used.

Sample SAS® code is provided below:

```
*****

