** CHG = Change in LDL-C from Baseline to Week 12      **
** TRT = Treatment group where 0 = placebo, 1= MGL-3196           **
** BASE = Baseline LDL-C                                     **
*****
PROC GLM;
```

```
CLASS TRT;  
MODEL CHG = TRT BASE;  
LSMEANS TRT / e pdiff=control("0") cl;  
RUN;
```

The same analysis models for Week 12 LDL-C are also used to analyse the percent change and change in LDL-C from baseline at Week 2 and Week 4 LOCF.

The primary efficacy analysis will be performed based on the Per Protocol Population to evaluate the robustness of the primary efficacy analysis.

Other imputation method for missing values of Week 12 LDL-C will be evaluated, including multiple imputation and Mixed Model for Repeated Measurements (MMRM) method based on the mITT population. The multiple imputation method will use statin group (80 mg Atorvastatin, 20/40 mg Rosuvastatin, or No/Low Dose Statin), baseline and all the post-baseline valid LDL-C values as references for the imputation with the monotone missingness assumption. The MMRM method will include treatment and visit as factors, and treatment by visit interaction.

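### The baseline-factor subgroup analyses of LDL-C give a p-value in each level but no estimate of whether the effect differs between levels, so unequal cell sizes can look like heterogeneity

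*SAP*

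**What the plan says.** SAP 3.7.3 introduces its list of factors with "The primary efficacy analysis of LDL-C will be repeated based on the following subgroups". The factors known at baseline are statin group (three levels), sex, baseline LDL-C (cut at 100 mg/dL), BMI (cut at 25 and, separately, at 30 kg/m²) and TSH averaged over screening and baseline (cut at 2 mIU/L). That makes six factors with 13 levels. A combined statin-by-LDL-C grouping is also listed.

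The analysis to be repeated is in SAP 3.7.2. Its code for percent change is "MODEL PCHG = TRT", with no subgroup term and no interaction. On output, the SAP says "The least-squares mean, 95% confidence interval, and p-value will be provided for the comparison of MGL-3196 versus placebo".

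The only interaction that the SAP plans for LDL-C belongs to a missing-data sensitivity analysis: "The MMRM method will include treatment and visit as factors, and treatment by visit interaction". Protocol 10.2.1.4 says only that "Subgroup analysis of the primary efficacy variable and/or selected secondary/other efficacy variables may be performed" and gives example factors; it mentions no interaction.

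On the status of these analyses, SAP 3.7.3 says: "Since the analyses are for descriptive purposes only, no adjustments will be made for multiplicity".

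**The concern.** A subgroup analysis asks whether the treatment effect differs between kinds of patient. A separate test in each level asks whether there is an effect in that level, and the power to answer depends on how many patients happen to fall there. If the true effect is the same everywhere, a large level will usually be significant and a small one often will not. Set side by side, the two results look like a drug that works in one group and not in the other.

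At stake is how this Phase 2 trial is read. An apparent dependence on statin type, baseline LDL-C or TSH could influence the design of later studies when it reflects only cell size. A multiplicity adjustment would not help, because the problem is unequal power and not the number of tests.

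**Working it through.** **Inputs.** SAP section 4: "Up to 105 patients in total will be randomized to 1 of 2 treatments (70 patients to MGL-3196, 35 patients to placebo". Protocol 10.2.4: the difference "between any dose of the MGL-3196 group and the placebo group is about -20" percent, with a common SD of 20%. Neither document gives subgroup sizes, so the splits below are assumptions shown as a range. Each split is applied equally in both arms, with cell sizes rounded.

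**The plan's own figure.** A two-sided two-sample t-test at 0.025 (noncentral t; difference 20, SD 20) has 91.0% power with 27 per group and 89.8% with 26. The stated 27 per group for 90% power is reproduced.

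**Power within a level.** For n active and m placebo patients, the noncentrality is 20 / (20 × √(1/n + 1/m)) on n + m − 2 degrees of freedom, tested two-sided at 0.05 to match the 95% CIs. For the whole trial (70 versus 35) the power is 99.8%.

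**Chance that exactly one of two levels is significant under a uniform effect.** The levels contain different patients, so this is p1(1 − p2) + p2(1 − p1).

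| Split | Cells (active v placebo) | Power | Exactly one significant |
|---|---|---|---|
| 50/50 | 35 v 18; 35 v 17 | 0.92; 0.91 | 15% |
| 70/30 | 49 v 25; 21 v 10 | 0.98; 0.71 | 30% |
| 80/20 | 56 v 28; 14 v 7 | 0.99; 0.54 | 46% |

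For example, the 80/20 row is 0.9895 × 0.4639 + 0.5361 × 0.0105 = 0.465. The 70/30 row depends slightly on rounding: cells of 49 v 24 and 21 v 11 give 27%.

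**Statin group, three equal levels** (23 v 12, 23 v 12, 24 v 11). The powers are 0.778, 0.778 and 0.760. P(all significant) = 0.460 and P(none) = 0.012, so P(mixed) = 1 − 0.460 − 0.012 = 53%.

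**Sensitivity.** If only 54 and 27 patients contribute (the 27 completers of the sample-size section, with 2:1 allocation kept), the three two-level figures become 28%, 41% and 59%. With a uniform 15-point effect and 70 versus 35 patients, they are 41%, 52% and 63%.

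**What an interaction estimate would give.** The SE of the overall effect is 20 × √(1/70 + 1/35) = 4.14 points. For a factor with a fraction f of patients in one level, the SE of the difference between level effects is 4.14 / √(f(1 − f)).

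- 50/50: SE 8.28; 95% half-width 1.96 × 8.28 = 16.2 points; difference detectable with 80% power (1.96 + 0.84) × 8.28 = 23.2 points.
- 80/20: SE 10.35; half-width 20.3 points; detectable difference 29.0 points.

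Under a uniform effect this contrast is significant at 0.05 in 5% of trials per factor, whatever the split.

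**The case against.** Four objections deserve an answer.

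**The plan already supplies what is needed.** A reader might infer that nothing in the planned output can address heterogeneity. The documents do not support that. Each level has an estimate with a 95% CI, and the levels of a baseline factor contain different patients, so the contrast and its SE can be derived. For the 80/20 split the level SEs are 4.63 and 9.26, and √(4.63² + 9.26²) = 10.35, the interaction SE found above. What stands is that the plan neither reports this contrast nor says how differences between levels will be judged.

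**The larger percentages depend on unstated splits.** This stands. For one evenly split factor at full enrolment the figure is 15%. Only baseline LDL-C has textual support for imbalance: Protocol 4.1 requires at least 100 mg/dL for entry, and SAP 3.7.4 expects some patients below that at baseline. For sex, BMI and TSH an uneven split is conjecture.

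**The analyses are labelled descriptive.** This lowers the importance of the point. However, SAP 3.7.3 uses the label to waive multiplicity adjustment, not to remove the p-values. The table shells are in separate documents, so the final display cannot be seen.

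**An interaction at this size is weak.** For an even split, the difference detectable with 80% power (23.2 points) exceeds the whole assumed effect. Six independent unadjusted tests would give 1 − 0.95⁶ = 26% chance of at least one false flag. Both are reasons to report an estimate with its interval and not a bare test.

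A reader might also count every listed cell, 87 in all, as showing this fault. That is not supported. Sixty-eight of them cross exposure, SHBG or final-dose groups with a baseline factor. Those groups are formed after randomisation and only among active patients, so they have no placebo counterpart and raise a separate question.

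**Conclusion.** The point holds as a minor improvement to the analysis plan. For the six baseline factors, the SAP plans a p-value in each level and no estimate of the difference between levels. Under its own assumptions (uniform 20-point effect, SD 20, 70 versus 35 patients), discordant significance has a chance of 15% to 46% for two-level factors split between 50/50 and 80/20, and about 53% for three equal statin levels. These figures rest on assumed splits and full enrolment; fewer patients or a smaller true effect raises the two-level figures.

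The conclusion is that within-level significance can mislead about heterogeneity. It does not follow that it usually will for a balanced factor, or that the planned intervals are uninformative. The primary comparison is unaffected.

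**What to change.** For each baseline factor in SAP 3.7.3, fit one model on the whole mITT population: PCHG = TRT SUB TRT*SUB. Add no covariates unless the primary model has them. The SAP's percent-change model has none, whereas Protocol 10.2.1.1 specifies an ANCOVA with baseline LDL-C, so follow whichever is retained as primary. Report the interaction estimate with its 95% CI, and show the effect in each level, with its CI, from the same model. State in the SAP that heterogeneity is judged from the interaction estimate and not from within-level p-values, and that an interval including zero is not evidence of a consistent effect.

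The cost is a few lines of SAP text and one extra estimate per factor, or two for the three-level statin factor. No new data are needed. The drawback is imprecision: a half-width of about 16 points for an even split and about 20 for 80/20. Whether to keep the crossed exposure, SHBG and final-dose cells is a separate decision that this change does not settle.
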